#### Weaning

Since the time a patient achieves unassisted ventilation affects some secondary endpoints, and because recent evidence-based consensus recommendations have identified a best practice for weaning, a weaning strategy will also be controlled by protocol rules in accordance with these evidence-based recommendations. This will assure similar weaning methods and provide potential benefit to both study groups. This weaning strategy is a simplified version of the protocolized weaning strategy used in prior ARDS Network studies (Appendix D).

#### PEEP

As a study procedure, all study patients will receive a high PEEP strategy based on previously deployed PEEP protocols [27-30]. The use of the high PEEP protocol will be required for up to 5 days after randomization. We selected to protocolize high PEEP in all patients for the following reasons:

1. To mitigate the possibility of differential PEEP use between arms.
2. A presumptive physiologic benefit of neuromuscular blockade is reduction of atelectrauma, barotrauma, volutrauma, and heterogeneity in alveolar expansion. A

higher PEEP strategy will limit atelectrauma and heterogeneity of alveolar expansion. It is also unknown if neuromuscular blockade adds additional protection over a higher PEEP strategy alone.

3. Trials should test novel interventions on a background of “best care”. Secondary analyses and opinion leaders suggest high PEEP strategies may be beneficial in those ARDS patients with higher acuity.[15]

If hypotension occurs with the use of a high PEEP protocol, the recommendation from the fluid management approach will be the administration of fluid boluses. (Appendix E)

We will allow deviation from the high PEEP strategy, for limited situations:

- If there is clinical concern that the use of high PEEP may be worsening oxygenation (e.g., oxygenation worsens with PEEP increases) at a  $FiO_2 \geq 0.5$  for more than 2 hours, clinicians may trial lower PEEP.
- If oxygenation worsens or is unchanged at the lower level of PEEP, the PEEP should be raised back to the previous level.
- If oxygenation improves, the clinicians may choose to leave the PEEP at the lower level. Subsequently the clinician should decrease the  $FiO_2$  as tolerated until a listed combination on the PEEP/ $FiO_2$  chart is reached, and then continue to follow the PEEP/ $FiO_2$  protocol.
- If hypotension, high plateau pressure ( $> 30$  cm H2O), and/or severe acidemia ( $pH < 7.15$ ) are present despite further tidal volume reduction, fluid boluses, and/or respiratory rate increase (Section 5.3.3. and Appendix D1), lower PEEP may be used. With the ROSE PEEP table (Appendix D1) as the starting point, reduce PEEP 2 cm H2O every 5-15 minutes, until the physiologic parameters of concern have improved, as per the treating clinician and/or responsible investigator (e.g., reduce PEEP to the level that lowers plateau pressure to 30 cm H2O). Later, try to return PEEP to a level consistent with the ROSE PEEP table, at least daily through study day 5.

Lower PEEP may also be used if a study participant develops a pneumothorax, or is deemed at high risk for barotrauma (e.g., known multiple pulmonary cysts or bullae).

#### 5.3.4 ON-STUDY FLUID MANAGEMENT

Fluid management during shock will be unrestricted. However, in patients not in shock, a conservative fluid approach will be recommended for all patients enrolled in the study. This conservative fluid management approach will represent a simplification of the algorithm utilized in the ARDS Network FACTT study (see Appendix E)[31].

#### 5.3.5 GLUCOSE CONTROL

Hyperglycemia has been associated with neuromuscular dysfunction. Each site will use their own standard management, including institution-specific insulin drip protocols, to maintain blood

sugars with a target upper blood glucose level  $\leq$  180 mg/dL. This range avoids marked hyperglycemia, while minimizing the risk of both iatrogenic hypoglycemia and other harms associated with a lower blood glucose target.

### 5.3.6 RESCUE PROCEDURES

If PaO2  $\geq$  55 mmHg or SpO2  $\geq$  88% with FIO2 of 1.0 cannot be maintained, clinicians may employ alternate therapies (rescue procedures). Rescue procedures will be chosen according to the practice at the clinical site, and may include repeated recruitment maneuvers, prone positioning, inhaled nitric oxide, inhaled epoprostenol sodium, high frequency ventilation, or ECMO. The participants will continue to be followed and included in the analysis on an intention-to-treat basis. The use of rescue procedures will constitute a secondary outcome.

## 6 DATA VARIABLES AND SPECIMENS

### 6.1 BACKGROUND ASSESSMENTS

1. Demographic and Admission Data (including age, sex, race)
2. Pertinent Medical History and Physical Examination (including Charlson co-morbidity score)
3. Height; gender; measured Body Weight (mBW); calculated predicted body weight (PBW); body mass index (BMI)
4. Time on ventilator prior to enrollment
5. Type and location of endotracheal intubation
  - Pre-hospital, ED, ward, ICU, operation room, referring hospital
6. Location when inclusion criteria met
  - Pre-hospital, ED, ward, ICU, operation room, referring hospital
7. Type and location of ICU Admission
  - Medical
  - Surgical scheduled
  - Surgical unscheduled
  - Trauma
8. Risk factors for ARDS (sepsis, aspiration, trauma, pneumonia, other)
9. Ever smoker (>100 cigarettes in lifetime)?
  - If Yes, current smoker?
  - If ever smoker, estimate pack years [Pack years = (# packs per day) x (number of years smoked)]
  - If former smoker, when quit?

10. Survey of alcohol history (see Appendix I)

11. Basic assessment of prior functioning

## 6.2 BASELINE ASSESSMENTS

The following information will be recorded during the 24-hour interval preceding randomization. If more than one value is available for this 24-hour period, the value closest to the time of randomization will be recorded. If no values are available from the 24 hours prior to randomization, then values will be measured post randomization but prior to initiation of cisatracurium (intervention arm) and within 4 hours (control arm). All values will be derived from clinically available data.

1. History and physical examination

Vital signs: heart rate (beats / min), systemic systolic and diastolic BP (mmHg), body temperature (°C) (APACHE)

2. Ventilator mode, set rate, actual rate, minute ventilation, tidal volume, FiO2, PEEP, I:E ratio, plateau, peak, and mean airway pressures

3. Administration of the following medications (name)

a) Intravenous sedatives

b) Intravenous opioids

c) Intravenous or enteral Corticosteroids (>= 20 methylprednisolone equivalents)

4. Presumed site of infection, if sepsis is the etiology of ARDS

5. APACHE III score, including the acute physiology components and laboratory values

6. APACHE III demographics plus history of: hypertension, prior myocardial infarction, congestive heart failure, peripheral vascular disease, prior stroke with sequelae, dementia, chronic pulmonary disease, arthritis, peptic ulcer disease

7. SOFA Score: Cardiovascular, renal, respiratory, hepatic, and hematology organ function will be assessed using the SOFA methodology as described in Appendix K.

8. Pneumothorax at time of randomization (Y/N)

## 6.3 ASSESSMENTS DURING STUDY

### 6.3.1 HEMODYNAMIC MONITORING DURING STUDY STARTUP

For the first 4 hours after randomization, we will record the time that target PEEP/FiO2 and sedation score are achieved, the time of both the cisatracurium bolus and infusion, as well as the time of any fluid bolus or change in vasopressor use.

Together with SOFA and adverse event data at 48 hours, this hemodynamic monitoring data will be used to report study process safety data to the DSMB.

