#### 4.4 RANDOMIZATION, AND STUDY INITIATION TIME WINDOW

All patients must be randomized within 48 hours of meeting inclusion criteria. The window for randomization begins at the time of meeting all inclusion criteria, regardless of patient location.

After randomization, the low tidal volume protocol must be initiated within two hours (if not already being used). In the intervention arm, deep sedation followed by neuromuscular blockade must be initiated within four hours of randomization.

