## 5.1 EARLY NEUROMUSCULAR BLOCKADE GROUP

### 5.1.1 INITIATION AND DOSAGE

Study staff will ensure a Ramsay score of 5-6 (RASS of -4 to -5, or Riker of 1-2) is achieved and documented prior to initiation of neuromuscular blockade and that patients are receiving controlled modes of mechanical ventilation. We do not mandate sedative type or dose.

Initiation of neuromuscular blockade must begin within 4 hours of randomization. Patients randomized to the early neuromuscular blockade arm will receive a cisastracurium besylate bolus of 15 mg, followed by a continuous infusion of 37.5 mg/hour for 48 hours (Appendix J).

We chose this fixed, relatively high dosage for simplicity (train of four titration imperfect and with limited evidence base [24-26]) and to help ensure effective neuromuscular blockade (clinical observation and train of four monitoring can lead to under-dosing). This dosage is the same as used in the ACURASYS trial. We chose cisatracurium as its metabolism is independent of hepatic and renal function.

In the rare circumstance that neuromuscular blockage is deemed inadequate, (i) check the patient and the ventilator to confirm the correct reading, (ii) check the infusion rate and drug to confirm correct, (iii) rebolus, using the below recommendation and call the CCC for further direction as needed.

Recommendation: If the end-inspiratory plateau pressure remains greater than 32 cm of water for at least 10 minutes, it is recommended that the patient receive the administration of increasing doses of sedatives and decreasing tidal volume and positive end-expiratory pressure (if tolerated) before considering using open-labeled cisatracurium. If the treating physician still wants to administer a neuromuscular blocking agent, an open-label, rapid, intravenous injection of 20 mg of cisatracurium will be recommended for patients in the control or treatment arms of the study. If this rapid, intravenous injection results in a decrease of the end-inspiratory plateau pressure by less than 2 cm of water, a second injection of 20 mg of cisatracurium will be allowed. If after injection, the end-inspiratory plateau pressure does not decrease or decreases by less than 2 cm of water, cisatracurium boluses should not be administered again during the following 24-hour period.

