## 5.3 COMMON STRATEGIES FOR BOTH STUDY GROUPS

### 5.3.1 STUDY STARTUP PROCEDURES

In both groups, we will use the following standardized, step-wise, startup procedures to collect hemodynamic safety data (Section 6.3.1) in the first 6 hours following randomization. These procedures will allow comparison of hemodynamics during study startup between groups, and will avoid simultaneous PEEP and sedation titration, which would render interpretation of hypotensive episodes challenging. Close oversight of study initiation should be provided by an intensive care attending and/or designee.

1. Initiate low tidal volume ventilation within 2 hours, as per Section 5.3.3.).
2. Adjust sedation to target sedation score (if not already at target) – deep sedation in the early neuromuscular blockade group, recommendation of light sedation in control group.

3. If in the neuromuscular blockade arm, start cisatracurium within 4 hours of randomization, as per section 5.1.1.
4. Before increasing PEEP, a PETAL investigator or designee will determine hemodynamic appropriateness for PEEP increase using the following as guidelines: MAP > 55 or SBP > 80, no fluid bolus or vasopressor increase for greater than 15 minutes.
5. Peep will be gradually up-titrated as per Appendix D1.

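### Protocol 5.3.1 promises 6 hours of start-up hemodynamic safety data but 6.3.1 records only 4, so late cisatracurium starters can have little or no timed record after drug start

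*Protocol*

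**What the plan says.** Two sections of the protocol describe one data set and give it different lengths.

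- Section 5.3.1 (study startup procedures) says that both groups follow standardized "startup procedures to collect hemodynamic safety data (Section 6.3.1) in the first 6 hours following randomization". It gives the purpose as comparing start-up hemodynamics between groups, and it keeps sedation and PEEP titration apart so that hypotension can be interpreted.
- Section 6.3.1, the section cited there, reads: "For the first 4 hours after randomization, we will record the time that target" PEEP/FiO2 and sedation score are achieved. It adds the times of the cisatracurium bolus and infusion, "as well as the time of any fluid bolus or change in vasopressor use". These data, with SOFA and adverse event data at 48 hours, go to the DSMB as process-safety information.

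The time limit for the drug is the same wherever it appears. Section 4.4 says that "deep sedation followed by neuromuscular blockade must be initiated within four hours of randomization", section 5.1.1 that "Initiation of neuromuscular blockade must begin within 4 hours of randomization", and step 3 of section 5.3.1 repeats it: "If in the neuromuscular blockade arm, start cisatracurium within 4 hours of randomization, as per section 5.1.1". Step 4 then begins: "Before increasing PEEP, a PETAL investigator or designee will determine hemodynamic appropriateness for PEEP increase". Step 5 is the gradual up-titration of PEEP under Appendix D.1.

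No other text resolves the window. The time-events schedule in Appendix B has no row for start-up hemodynamics, and the SAP does not list timed fluid boluses or vasopressor changes among its variables.

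**The concern.** A site that follows 6.3.1 stops recording at the same hour that is the latest permitted start for the drug. PEEP up-titration comes after the drug in the numbered order, so for a late starter the record can close before either exposure has been observed. The protocol itself names hypotension as a risk of the accompanying deep sedation (section 9.1) and, historically, of high PEEP (section 9.2). A timed record of boluses and vasopressor changes is meant to show whether such events follow these steps.

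At stake is the completeness of a safety report to the DSMB, and whether sites record over the same period. With two instructions, some sites may stop at 4 hours and others at 6.

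**Working it through.** **Inputs.** Recording window: 4 h (6.3.1) or 6 h (5.3.1), both counted from randomization. Latest cisatracurium start: 4 h (4.4, 5.1.1, 5.3.1 step 3). Order of steps: sedation, cisatracurium, hemodynamic check, PEEP up-titration (5.3.1 steps 2 to 5). Pace of adjustment: one step every 5–15 minutes, a step being 2 cm H2O of PEEP and/or 0.1 of FiO2 (Appendix D.1).

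**Recorded time after drug start** = window − start hour.

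| Drug start (h after randomization) | 4-h window | 6-h window |
|---|---|---|
| 1 | 4 − 1 = 3 h | 6 − 1 = 5 h |
| 2 | 4 − 2 = 2 h | 6 − 2 = 4 h |
| 3 | 4 − 3 = 1 h | 6 − 3 = 3 h |
| 4 | 4 − 4 = 0 h | 6 − 4 = 2 h |

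The difference is always 2 h. It matters most for starts near the limit, where the 4-hour window leaves almost nothing.

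**PEEP titration, as an illustration.** The documents do not say how large a PEEP rise a typical patient needs. Assume 10 cm H2O, for example from 8 (the eligibility floor) to 18 (a value in the Appendix D.1 table at FiO2 0.50).

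- Number of steps: 10 / 2 = 5.
- Duration at one interval per step: 5 × 5 = 25 minutes to 5 × 15 = 75 minutes.
- If titration begins as soon as the drug is started at hour 4, it ends between 4 h 25 min and 5 h 15 min.

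That is wholly outside the 4-hour window and wholly inside the 6-hour one. A smaller rise takes less time but, after an hour-4 start, still falls after recording has closed. The guideline in step 4 asks for more than 15 minutes without a fluid bolus or vasopressor increase before PEEP is raised, so patients with hemodynamic events would tend to have PEEP titrated later still.

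**What other data collection retains.**

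- Section 6.3.2 collects the loading-dose time and infusion start without a 4-hour limit.
- Appendix B has daily modified SOFA (systolic pressure and vasopressor use) and daily fluid intake and output.
- Section 11.1 collects hypotension as an adverse event, through day 7 or ICU discharge, if the investigator judges it related to high PEEP or of uncertain relationship. Appendix C3 otherwise generally exempts the need for fluids or vasoactive drugs for hypotension, unless it is judged study-related or of uncertain relationship.

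None of these gives the clock time of a bolus, a vasopressor change or target PEEP after hour 4. The adverse event route also depends on the investigator's attribution in an unblinded trial.

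**The case against.** The strongest reply is that the mismatch is real but its consequences are easily overstated. A reader might infer that the 4-hour limit biases the comparison by understating hemodynamic events in the active arm. The documents do not support that, for four reasons.

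- Both arms are observed over the same 0–4 hours, and both lose hours 4–6. That only the active arm loses time after dosing is true by definition, since controls receive no study dose. Controls also have sedation and PEEP steps, and no deadline for reaching target PEEP is set in either arm.
- Section 9.1 attributes hypotension needing vasopressors to deep sedation, which must be reached before the drug starts. With the drug started by hour 4, the deepening of sedation falls largely inside the 4-hour record.
- The documents give no distribution of drug-start or target-PEEP times. A patient who starts at hour 1 keeps 3 hours of record even under 6.3.1.
- Appendix D.1 lets PEEP, FiO2 or both be adjusted to reach the scale, so the PEEP rise needed may be smaller than the 10 cm H2O assumed here. It also speaks of settings off the scale immediately after randomization, which could suggest earlier titration, although 5.3.1 orders PEEP after the drug.

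These points stand against a claim of directional bias. They leave the contradiction intact. One could try to read the 6 hours as the span of the procedures and not of the recording, but 5.3.1 ties that figure to data collection and cites 6.3.1 by number. Partial capture elsewhere limits the loss but does not replace the time-stamps.

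A further fair point is that a 6-hour window counted from randomization still gives unequal time after drug start: 2 hours for a start at hour 4, 5 hours for a start at hour 1. It makes the plan consistent and gives every patient started within the limit at least 2 hours. It does not equalize follow-up.

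**Conclusion.** The two sections contradict each other, and the shorter window is the less suitable for the stated purpose. Under 6.3.1 as written, a start at the permitted limit leaves no timed post-start record, against 2 hours under 5.3.1. These figures rest only on the protocol's own time limits. The 25–75 minute titration time rests on the assumed 10 cm H2O rise.

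The loss may be greater in the intervention arm, because only that arm has the drug step and mandated deep sedation before PEEP titration. Its size, and the direction of any effect on the between-arm comparison, cannot be determined from the documents. The problem is confined to safety-data collection and the DSMB report, and the SAP does not use this data set.

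**What to change.** Reconcile sections 5.3.1 and 6.3.1 by changing 6.3.1 to record all its listed items through 6 hours after randomization in both arms, as 5.3.1 already states. Report the DSMB start-up comparison over that common window. Shortening 5.3.1 to 4 hours would also remove the contradiction, but it would make the gap for late starters permanent.

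The change concerns data recording only and alters no element of care. It costs a wording amendment and two more hours of time-stamps on an existing form.

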### 6.3.2 REFERENCE MEASUREMENTS

The following data will provide the basis for assessing protocol compliance and safety as well as between-group differences in several efficacy variables. Data for each of the variables will be recorded on the days shown in the Time-Events schedule (Appendix B) or until death, or discharge from the intensive care unit. Values will be derived from clinically available data.

1. NMB Dosing
  - a) Intervention Arm
    - i. Time and dose of loading dose
    - ii. Time of initiation of cisatracurium continuous infusion
    - iii. Reason and duration of infusion hold during first 48 hours
    - iv. Total dose of cisatracurium infusion during first 96 hours
    - v. Name and total dose of other NMB during first 96 hours
    - vi. Addition NMB administered after 96 hours (yes/no)
  - b) Control Arm
    - i. Name and total dose of any NMB used in the first 96 hours after randomization
    - ii. Addition NMB administered after 96 hours (yes/no)

#### Reference Measurements (Daily)

The following parameters will be measured and recorded between 4:00 and 10:00 A.M. using the values closest to 8:00 A.M. on the days specified in the Time-Events schedule. The following conditions will be ensured prior to measurements: no endobronchial suctioning for 10 minutes; no invasive procedures or ventilator changes for 30 minutes. All vascular pressures will be zero-referenced to the mid-axillary line.

1. If receiving positive pressure ventilation: Ventilator mode, set rate, actual rate, minute ventilation, tidal volume, FiO2, PEEP, I:E ratio, plateau, peak, mean airway pressures, set peak flow, and set inspiratory time
2. PaO2, PaCO2, pH, and SpO2

Values for the following variables will be recorded for the dates shown in the Time-Events Schedule. If the measurements are not obtained during the 6-hour reference interval (4:00 to 10:00 A.M.), then the value obtained closest in time to the reference interval on the respective date will be recorded. If more than one value is obtained during the reference interval, then the value obtained closest to 8:00 A.M. will be recorded.

3. Rescue procedures used
  - a) Proning
  - b) Inhaled nitric oxide
  - c) Epoprostenol sodium
  - d) High frequency ventilation

- e) ECMO
- 4. Serum electrolytes and glucose
- 5. Administration of the following medication infusions:
  - a) Intravenous sedatives
  - b) Intravenous opioids
  - c) Enteral or intravenous corticosteroids ( $\geq$  20 methylprednisolone equivalents)
- 6. Sedation score: If RASS  $<$  -1 (or Riker  $<$  3, Ramsay  $>$  3), and sedation given, list reason given
- 7. Was a sedation interruption performed? Y/N
- 8. Modified SOFA
- 9. Fluid intake and output/CVP if available
- 10. ICU Mobility Scale: Score 0-10 (see Appendix M)

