#### 2. IL-6 levels (plasma)

We will measure interleukin-6 (IL-6) at study entry and at 48 hours. A proposed mechanism of benefit of neuromuscular blockade is decreased ventilator-induced lung injury. Interleukin-6 is a pro-inflammatory cytokine that decreased in patients treated with a lung-protective low tidal volume ventilation strategy compared to control patients.[7] Furthermore, in pilot studies neuromuscular blockade was associated with decreased levels of IL-6.[13] Here, we hypothesize that compared to control subjects, subjects receiving neuromuscular blockade for 48 hours will have lower levels of IL-6, reflecting decreased ventilator-induced lung injury. As in the ARDS Network trials, analysis of covariance (ANCOVA) will be used to examine the impact of treatment with neuromuscular blockade on biomarker levels at 48 hours.

#### 3. Hospital mortality to day 28

#### 4. Ventilator free days to day 28

Ventilator free days to day 28 are defined as the number of days from the time of initiating unassisted breathing to day 28 after randomization, assuming survival for at least two consecutive calendar days after initiating unassisted breathing and continued unassisted breathing to day 28. If a patient returns to assisted breathing and subsequently achieves unassisted breathing to day 28, VFDs will be counted from the end of the last period of assisted breathing to day 28. A period of assisted breathing lasting less than 24 hours and for the purpose of a surgical procedure will not count against the VFD calculation. If a patient was receiving assisted breathing at day 27 or dies prior to day 28, VFDs will be zero. Patients transferred to another hospital or other health care facility will be followed to day 28 to assess this endpoint.

5. Organ failure free days to day 28

Organ failure is defined as present on any date when the most abnormal vital signs or clinically available lab value meets the definition of clinically significant organ failure according to SOFA scores (Appendix K).[21] Patients will be followed for development of organ failures to death, hospital discharge or study day 28, whichever comes first. Each day a patient is alive and free of a given organ failure will be scored as a failure-free day. Any day that a patient is alive and free of all organ failures will represent days alive and free of all organ failure.

6. ICU-free days at day 28

7. Hospital-free days at day 28

8. Physiologic measures to include:

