## B TIME-EVENTS SCHEDULE

Measurement/Event	Day 0	1	2	3	4	5	6	7	14	21	28	90
Demographics, History and Physical	X											
Etiology of ARDS	X											
APACHE III	X											
HCG (females)	X											
Alcohol Use/Smoking History	X											
CXR (number of quadrants)	X											
Study NMB Administration	X	X	X									
Baseline LTO	X											
Non-protocol NMB administration	X	X	X	X	X							
Level of Sedation	X	X	X	X	X	X	X	X				
Sedation Interruption (y/n)	X	X	X	X	X	X	X	X				
Gross motor assessment				X								
ICU Mobility Scale		X	X	X	X	X	X	X	X	X	X	
Ventilator Parameters#†	X	X	X	X	X			X				
Arterial Blood Gases	A	A	A	A	A			A				
K+, HCO 3 , glucose	A	A	A	A	A			A				
Pneumothorax (y/n)*	X										X	
Use of rescue procedures (y/n)*											X	
Fluids (intake/output)	X	X	X	X	X	X	X	X				
Central Venous Pressure	A	A	A	A	A	A	A	A				
On-study meds: sedative, opioid, corticosteroid administration (y/n)	X	X	X	X	X			X				
SOFA Score (modified) B	X	X	X	X	X	X	X	X	X	X	X	
Manual Muscle Testing (with screening)								X	X	X	X	
Paralysis recall assessment**											X	
Plasma Collection	X	X	X									
Urine Collection	X	X	X									
Whole Blood collection for DNA/RNA	X		X									
Vital Status§											X	X

X=Required

A=When available

†= Data gathered at times indicated or until 48 hours UAB, whichever occurs first

\*\*=Collected once during study hospitalization

B=Records clinically available creatinine, platelets, bilirubin, SBP and vasopressor use

~=Data gathered on days 0-28 or until d/c from study hospital

#=Measure during reference period (0600-1000); other values may be obtained closest to 0800 on the specified calendar date

§=Also measure at 6 and 12 months as part of Long Term Outcome.

\*= Assessed for days 1-28 once on day 28 or discharge

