## K SOFA SCORING SYSTEM

Variables	SOFA Score				
	0	1	2	3	4
Coagulation Platelets x 10  /μL	>150	≤150	≤100	≤50	≤20
Liver Bilirubin, mg/dL	<1.2	1.2-1.9	2.0-5.9	6.0-11.9	>11.9
Cardiovascular Hypotension	No hypotension	Mean arterial pressure <70 mmHg	Dop ≤5 or dob (any dose) ‡	Dop >5, epi ≤0.1, or norepi ≤0.1‡	Dop >15, epi >0.1, or norepi >0.1‡
Renal Creatinine, mg/dL or urine output, ml/d	<1.2	1.2-1.9	2.0-3.4	3.5-4.9 or <500	>4.9 or <200

\*Norepi indicates norepinephrine; Dob, dobutamine; Dop, dopamine, Epi, epinephrine.

†Values are with respiratory support.

‡Adrenergic agents administered for at least one hour (doses given are in μg/kg/min)

We define a clinically significant organ failure as a new SOFA score of ≥ 2.

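### Organ failure is defined by each date's worst value, but section 6.3.2 puts Modified SOFA under an 8 A.M. recording rule, and oliguria that starts after day 7 has no scheduled source

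*Protocol*

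**What the plan says.** The endpoint is organ-failure-free days to day 28, a secondary outcome.

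- **Definition.** Protocol 3.9.2, item 5: "Organ failure is defined as present on any date when the most abnormal vital signs or clinically available lab value meets the definition". SAP Appendix A3 uses the same wording, and SAP Appendix A1 assigns a t-test.
- **Threshold.** Protocol Appendix K: "We define a clinically significant organ failure as a new SOFA score of" 2 or more. The cardiovascular component reaches 2 only with a listed adrenergic agent given for at least one hour. The criterion "Mean arterial pressure <70 mmHg" alone scores 1.
- **Recording rule.** Protocol 6.3.2, Reference Measurements (Daily), sets a 4:00 to 10:00 A.M. window for a list in which Modified SOFA is item 8: "If more than one value is obtained during the reference interval, then the value obtained closest to 8:00 A.M. will be recorded". The sentence before it says that a measurement not obtained in the window is replaced by the one nearest in time to the window on that date.
- **Schedule.** Protocol Appendix B puts SOFA on days 0 to 7, 14, 21 and 28, with its own footnote: "Records clinically available creatinine, platelets, bilirubin, SBP and vasopressor use". That footnote gives no time of day. The 8 A.M. footnote, "Measure during reference period (0600-1000); other values may be obtained closest to 0800 on the specified calendar date", is marked on the ventilator row in the table as it reads to us.
- **Urine output.** In Appendix K and SAP Appendix A3 the renal component scores 3 at "3.5-4.9 or <500" ml/day and 4 below 200 ml/day. The SOFA footnote omits urine output. It can come only from the separate item "Fluid intake and output/CVP if available", which Appendix B schedules on days 0 to 7.

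**The concern.** When a date has several values, a coordinator cannot follow both 3.9.2 and 6.3.2: one asks for the worst value and the other for the value nearest 8 A.M. Sites could resolve this differently, and the SAP would then analyse a mixture under one name.

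Vasopressor use is where the choice matters most, because it starts and stops within a day. Protocol 9.1 names hypotension requiring vasopressor support as a risk of the deep sedation that accompanies blockade. Timed vasopressor changes are recorded only for the first 4 hours (6.3.1). Appendix C3 exempts the need for vasoactive drugs from adverse-event reporting unless the event is judged related or of uncertain relationship. Section 6.3.1 also sends SOFA data at 48 hours to the DSMB. So SOFA is one of the main structured records of vasopressor use after startup, and its recording rule should not be left open.

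**Working it through.** The documents give no event rate, SD, effect size or power for organ-failure-free days, so there is no stated figure to reproduce. The working compares the two rules.

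**Direction.** On any date the worst value is at least as abnormal as the value nearest 8 A.M. Carrying the last observation forward (SAP Appendix A3) preserves that order. The literal 6.3.2 rule therefore gives organ-failure days equal to or fewer than the definition does, never more.

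**Size for one episode.** Inputs: an episode of h hours, with D = h/24 days. Its start time is assumed uniform over the day, since the documents give no episode data. SOFA is recorded daily, as on days 1 to 7.

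- Worst-value rule: expected dates touched = D + 1.
- 8 A.M. rule: expected dates with 8:00 inside the episode = D.
- Expected loss = (D + 1) − D = 1 date.
- Chance that the episode is missed entirely = 1 − h/24 for h < 24, otherwise 0.

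| Duration | Dates, worst value | Dates, 8 A.M. | Missed entirely |
|---|---|---|---|
| 1 h | 1.04 | 0.04 | 96% |
| 6 h | 1.25 | 0.25 | 75% |
| 12 h | 1.50 | 0.50 | 50% |
| 24 h | 2.00 | 1.00 | 0% |
| 48 h | 3.00 | 2.00 | 0% |

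A simulation of 400,000 episodes per duration gives losses between 0.998 and 1.002 date, in agreement.

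**Where the loss is smaller.**
- For an episode already present at baseline, only the final date can differ, and only if the episode ends before 8:00: 8/24 = 0.33 date.
- For a component with one clinical value on that date, the loss is 0, because 6.3.2 records that value whatever its time.
- For days free of all organ failure, the loss is 0 on any date when another organ is already recorded as failed.
- For hypotension without a listed adrenergic agent, the loss is 0, because it scores 1 against a threshold of 2 under either rule.

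**After day 7.** SOFA is scheduled weekly. A 6-hour episode touches a scheduled date with probability 1.25/7 = 18%, so even the worst-value rule misses about 82%. The 75% figure does not describe this period.

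**Effect on the arm comparison.** Shift in the difference = loss per episode × difference between arms in episodes per patient. With equal episode numbers and timing in the arms, the shift is 0 and both means move together.

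**Urine output.** Creatinine of 2.0 mg/dL or more already scores at least 2, so urine output decides the renal score only when creatinine is below 2.0. On days 0 to 7 a source exists, although no text says that it feeds the renal score. If it does, oliguria present on day 7 can be carried forward under the SAP. What has no scheduled source is oliguria that begins after day 7 with creatinine below 2.0.

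**The case against.** The best defence is that 6.3.2 states a general default and the endpoint has its own rule in 3.9.2 and SAP Appendix A3. The same list holds items that cannot sensibly be 8 A.M. readings: rescue procedures, sedation interruption, fluid balance, and mobility, which 3.9.2 wants at its highest level. The Appendix B footnote for SOFA sets no time. The fallback sentence in 6.3.2 might even capture an afternoon vasopressor run if nothing was recorded in the window.

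Much of this stands. It means the documents are ambiguous, and a reader who infers that the collected data do undercount goes further than they allow. It does not remove the conflict. Creatinine, platelets, bilirubin and blood pressure are quantities for which an 8 A.M. value makes good sense, and section 6.2 already takes a single value, the one nearest randomization, at baseline. The fallback also leaves open whether no vasopressor running at 8:00 counts as a value obtained.

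Three stronger readings are tempting and unsupported.
- **That most short hypotensive episodes are lost.** Low pressure alone never reaches the threshold; only short adrenergic use can be lost.
- **That the rule would hide an arm difference in safety.** Vasopressor changes in the first 4 hours are timed separately, and section 8 lists blood pressure and vasopressor use among once-daily data. A shift of about one standard error can be constructed: with an assumed SD of 10 to 11 days, SE = SD × √(2/704) = 0.53 to 0.59 day, against 0.5 day from an assumed excess of 0.5 episode per patient. That excess is 0.5 × 704 = 352 episodes in one arm, and neither input is in the documents.
- **That urine output is not collected at all.** It is scheduled to day 7.

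**Conclusion.** The point holds as a conflict between two stated rules for a named secondary outcome, with a third description in Appendix B that does not settle it. If 6.3.2 is applied literally, the bias runs one way. On the daily-recording days it costs up to about one date per on-study episode, 0.33 for an episode present at baseline, and none for a component with a single value that date. Vasopressor runs of 6 and 12 hours are missed about 75% and 50% of the time. These sizes rest on uniform timing. Whether any loss occurs depends on how sites read 6.3.2, and whether it alters the treatment comparison depends on episodes differing by arm. The documents show neither. The urine-output gap is real but narrow. The primary outcome and the sample size of 1408 are untouched. Correction is worthwhile because it is cheap and the endpoint is otherwise not uniquely defined.

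**What to change.** 1. Remove Modified SOFA from the 8 A.M. list in Protocol 6.3.2. State there and in the Appendix B footnote that each scheduled SOFA date records that date's most abnormal creatinine, platelets and bilirubin, and any listed adrenergic agent given for at least one hour at any time on that date.
2. For urine output, either record the 24-hour volume on SOFA days 14, 21 and 28, or drop it from the modified score in Appendix K and SAP Appendix A3. On days 0 to 7, if it is kept, say that recorded fluid output supplies it.
3. If 8 A.M. values have already been collected, redefine the endpoint in SAP Appendix A3 as organ failure at the 8 A.M. reading and label it so in reports.

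A dialysis yes/no field would not help: the SOFA table has no dialysis criterion, so it would change no score.

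The cost is wording in 6.3.2, the Appendix B footnote and possibly Appendix K and SAP Appendix A3, plus at most one form field. The values come from existing charts.
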